4.1 List of Tables, Listings and Figures

4.2 Tables

Table Number	Table Title (Population)	Template
14.1.1	Subject Disposition (All Screened Subjects)	Appendix 2
14.1.2.1	Subject Demographics and Baseline Characteristics (Safety Population)	Appendix 2
14.1.2.2	Subject Demographics and Baseline Characteristics (ITT Population)	14.1.2.1
14.2.1.1	Frequency of Combined Score by Phase, Visit and Treatment and Maximum Combined Score (ITT Population)	Appendix 2
14.2.2.1	Frequency of Dermal Response Score by Phase, Visit and Treatment and Maximum Dermal Response Score (ITT Population)	Appendix 2
14.2.2.2	Frequency of Superficial Irritation (other effects) Score by Phase, Visit and Treatment and Maximum Superficial Irritation (other effects) Score (ITT Population)	Appendix 2
14.3.1.1	Treatment emergent Adverse Event (Safety Population)	Appendix 2
14.3.1.2	Treatment emergent Adverse Event by Severity (Safety Population)	Appendix 2
14.3.1.3	Treatment emergent Treatment Related Adverse Event (Safety Population)	14.3.1.1
14.3.1.4	Treatment emergent Treatment Related Adverse Event by Severity (Safety Population)	14.3.1.2

4.3 Listings

Listing Number	Listing Title (Population)	Template
14.3.2.1	Listing of Deaths (Randomised Population)	16.2.7.1
14.3.2.2	Listing of Serious Adverse Events leading to Discontinuation (Randomised Population)	16.2.7.1
16.1.7	Randomisation information (Randomised Population)	Appendix 2
16.2.2	Individual Subjects Protocol Violation (Randomised Population)	Appendix 2

Document Name	gsk-207585-reporting-and-analysis-plan		
Type	Version	Document Identifier	Effective Date
eldo_controlled	0.1; CURRENT; Most-Recent; Reviewed	090032d580e125d0	
Reason For Issue			

Listing Number	Listing Title (Population)	Template
16.2.7.1	All Adverse Events (Randomised Population)	Appendix 2
16.2.7.2	All Adverse Events (Non randomised Subjects)	16.2.7.1

Note: If there are no data to display generate a null listing.

4.4 Top line Outputs:

Table/Listing Figure Number	Table/Listing/Figure Title (Population)
14.1.1	Subject Disposition (All Screened Subjects)
14.1.2	Subject Demographics (ITT Population)
14.2.1.1	Frequency of Combined Score by Phase, Visit and Treatment and Maximum Combined Score (ITT Population)
14.3.1.1	Treatment emergent Adverse Event (Safety Population)
16.2.7.1	All Adverse Events (Randomised Population)

 GlaxoSmithKline	Document Name	gsk-207585-reporting-and-analysis-plan		
	Type	Version	Document Identifier	Effective Date
	eldo_controlled	0.1; CURRENT; Most-Recent; Reviewed	090032d580e125d0	
Reason For Issue				

5 Appendix 2:

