9.3.3. Safety Analysis(es)

Adverse Events (AE) will be tabulated according to the current version of the MedDRA. Frequencies and percentages will be presented overall, for each system organ class, and for each preferred term. Summaries of treatment-emergent AEs, treatment-related AEs, AEs leading to discontinuation, and serious AEs will be completed. For treatment-related or treatment skin site related AEs, these will also be presented by product/test site.

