2.5.2 Safety

2.5.2.1 Adverse events and Serious Adverse Events

All adverse events (AEs) will be summarised by primary system organ class and preferred term.

Treatment emergent adverse events (TEAEs) will be summarized by the number and percentage of subjects having any adverse event, an adverse event in each System Organ Class, and each individual adverse event ([Table 14.3.1.1](#)). All TEAEs will also be tabulated by severity ([Table 14.3.1.2](#)). Treatment-emergent AEs suspected of a relationship to study medication and those causing study discontinuation will be presented in a similar manner ([Table 14.3.1.3](#)). For treatment-related AEs, these will also be presented by severity, if applicable ([Table 14.3.1.4](#)).

Additionally, all treatment-emergent adverse events will be listed.

Deaths occurring during treatment (if any) will be listed ([Listing 14.3.2.1](#)) by treatment, including the date and study day of death, and the principal cause of death. Non-fatal serious

Document Name	gsk-207585-reporting-and-analysis-plan		
Type	Version	Document Identifier	Effective Date
eldo_controlled	0.1; CURRENT; Most-Recent; Reviewed	090032d580e125d0	
Reason For Issue			

GSK Consumer Healthcare

Confidential

Page 12

Statistical Analysis Plan

207585

adverse events and adverse events causing study treatment discontinuation will be listed ([Listing 14.3.2.2](#)).

All AEs will be listed in the [Listing 16.2.7.1](#) and [Listing 16.2.7.2](#)

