2.8 Sample size calculation

Approximately 280 healthy subjects were screened to randomize at least 240 subjects to ensure 200 evaluable subjects complete the entire study. If no reaction is observed in 200 subjects, there is a 95% certainty that the actual rate of reactions in the wider population is <1.8%.

3 Changes to the Protocol Defined Statistical Analysis Plan

There were no changes or deviations to the originally planned statistical analysis specified in the [protocol version 1.0 \[\(Dated: 31/JAN/2017\)\]](#).

 GlaxoSmithKline	Document Name	gsk-207585-reporting-and-analysis-plan		
	Type	Version	Document Identifier	Effective Date
	eldo_controlled	0.1; CURRENT; Most-Recent; Reviewed	090032d580e125d0	
	Reason For Issue			

4 Appendix 1:

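### SAP 2.5.2.1 and the SAP output list disagree on Listing 14.3.2.2 and Table 14.3.1.3, and the serious-AE summary promised in the protocol has no table

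*SAP*

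**What the plan says.** **Protocol.** Section 9.3.3 commits to four groups of AE summaries: "Summaries of treatment-emergent AEs, treatment-related AEs, AEs leading to discontinuation, and serious AEs will be completed". The Statistical Methods part of the synopsis makes the same commitment.

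**SAP text.** Section 2.5.2.1 describes Listing 14.3.2.2 in a sentence broken by a page header. It follows the description of the deaths listing, "and the principal cause of death. Non-fatal serious", and continues "adverse events and adverse events causing study treatment discontinuation will be listed". For tables, the same section says "Treatment-emergent AEs suspected of a relationship to study medication and those causing study discontinuation will be presented in a similar manner" and points to Table 14.3.1.3.

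**SAP output list.** Section 4.3 titles Listing 14.3.2.2 "Listing of Serious Adverse Events leading to Discontinuation (Randomised Population". Section 4.2 titles Table 14.3.1.3 "Treatment emergent Treatment Related Adverse Event (Safety Population" and gives it the template of Table 14.3.1.1. The last AE table, 14.3.1.4, is "Treatment emergent Treatment Related Adverse Event by Severity (Safety Population".

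**Declared changes.** SAP section 3 says "There were no changes or deviations to the originally planned statistical analysis specified in the" protocol, version 1.0.

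**The concern.** The text of SAP 2.5.2.1 describes a listing with two groups in it: non-fatal serious AEs, and AEs that stopped study treatment. The title in SAP 4.3 describes only the overlap of seriousness and discontinuation. A programmer who works from the output list would leave out two kinds of event: a serious AE after which the subject continued, and a non-serious AE that made a subject stop.

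The tables have a similar problem. The text gives AEs causing discontinuation a home in Table 14.3.1.3, but the title and template of that table do not provide for them. Serious AEs have no table at all.

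General safety, through AE frequency and severity, is the trial's only secondary objective. The subjects are healthy volunteers, and the protocol keeps expected patch-site reactions out of the AE record while recording unexpected ones such as rash or hives. A non-serious event of that kind that ends participation is one that the listing, built as titled, would not show.

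**Working it through.** The plan gives no figure to reproduce on this point. The check is a comparison of the text, the output list, the templates and the protocol.

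**Step 1. Listing 14.3.2.2.** Let S be the non-fatal serious AEs and D the AEs that led to discontinuation.
- Text (SAP 2.5.2.1): S or D. Events listed = |S| + |D| − |S and D|.
- Title (SAP 4.3): S and D. Events listed = |S and D|. The title also drops the non-fatal restriction.

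Nothing else in the SAP settles which holds. The listing has no template of its own and borrows that of Listing 16.2.7.1. The programming notes there deal only with Listing 16.2.7.2 and give no selection rule for 14.3.2.2.

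The size of the difference depends on event counts that the documents do not give. With **assumed** counts, and all serious events taken as non-fatal:

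| Serious | Led to discontinuation | Both | As titled | As in the text |
|---|---|---|---|---|
| 2 | 4 | 1 | 1 | 2 + 4 − 1 = 5 |
| 1 | 3 | 0 | 0 | 1 + 3 − 0 = 4 |
| 3 | 5 | 2 | 2 | 3 + 5 − 2 = 6 |

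These rows show the logic only and are not a forecast for this trial.

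**Step 2. The four promised summaries against the SAP tables.**

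| Promised in protocol 9.3.3 | SAP 2.5.2.1 text | SAP 4.2 list and templates |
|---|---|---|
| Treatment-emergent AEs | Tables 14.3.1.1, 14.3.1.2 | Same |
| Treatment-related AEs | Tables 14.3.1.3, 14.3.1.4 | Same |
| AEs leading to discontinuation | Table 14.3.1.3 | 14.3.1.3 is titled for related events only, and its template has no discontinuation row |
| Serious AEs | No table named | No table |

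Two of the four agree, one is contradicted between text and list, and one is missing throughout. If Table 14.3.1.3 is built as titled, it omits unrelated AEs that caused discontinuation and does not mark the related ones that did.

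**Step 3. What remains visible.** Table 14.1.1 gives the number and percentage of randomised subjects who did not complete because of an AE. It is one overall count, without system organ class, preferred term or product. Listing 16.2.7.1 carries a *Serious?* and a *Withdrawn?* column for each AE in randomised subjects. Both are on the top-line list in SAP 4.4.

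**Step 4. The meaning of discontinuation.** SAP 2.5.2.1 refers to study discontinuation for the table and to study treatment discontinuation for the listing. The two need not coincide here: protocol 5.2 provides for induction patching to stop while the subject can still take part in the challenge phase. (That provision is triggered by patch-site scores, so it only shows that the two states are distinct.) The listing template has separate columns for action taken on study product and for withdrawal from the study, so the choice of variable changes what is selected.

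**The case against.** The strongest reply is that SAP 2.5.2.1 describes the listing correctly, that nothing makes a short title override the text, and that a careful programmer would follow the text. On this view the fault is loose titling.

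The reply also shows where stronger readings fail:
- A reader might infer that no table covers either group. That is not so: the text assigns AEs causing discontinuation to Table 14.3.1.3. For that group the fault is an inconsistency, not an omission.
- A reader might infer that no count of AE-related discontinuation is produced. Table 14.1.1 produces one, with a percentage.
- A reader might infer that an empty Listing 14.3.2.2 is likely and would pass for an absence of serious AEs and AE withdrawals. The documents give no basis for predicting an empty listing, and a reader would have to overlook both Table 14.1.1 and Listing 16.2.7.1 to be misled.
- A reader might infer that an unexpected rash leading to withdrawal disappears from the report. If treatment-emergent, it is counted in Tables 14.3.1.1 and 14.3.1.2, which have a skin-related row. Only its link to discontinuation is absent from the AE tables.

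Those limits stand. The conflict also stands, because text and list cannot both be followed and no order of precedence is stated. The missing serious-AE table is not a matter of titles, since the text names none either. A line listing with flags is not the summary that the protocol promised.

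**Conclusion.** The point holds as a minor reporting defect. Listing 14.3.2.2 has two incompatible specifications, and the one in the output list is too narrow. Table 14.3.1.3 is specified inconsistently for AEs causing discontinuation. The serious-AE summary promised in the protocol is not specified anywhere, and SAP section 3 does not declare this as a change.

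In size, one of four promised summaries is missing and one is contradictory. The effect on the listing cannot be quantified without event counts. It would matter only if outputs are built from the titles and if at least one event is serious without discontinuation, or leads to discontinuation without being serious. The primary endpoint is untouched and no AE data are lost.

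**What to change.** 1. Retitle Listing 14.3.2.2 *Non-fatal Serious Adverse Events and Adverse Events Leading to Discontinuation*. Select events that are (serious and not fatal) or that led to discontinuation. State whether discontinuation means stopping study treatment (the column for action taken on study product), withdrawal from the study (*Withdrawn?*), or either, and use one term throughout SAP 2.5.2.1. Say also whether a fatal event that carries the discontinuation flag appears here as well as in Listing 14.3.2.1. Selecting simply on serious or withdrawn would not do: it would admit all fatal events and would equate study withdrawal with treatment discontinuation.
2. Add a summary table of serious treatment-emergent AEs from the template of Table 14.3.1.1.
3. For AEs leading to discontinuation, either add a table from the same template and correct the reference to 14.3.1.3 in SAP 2.5.2.1, or change the title and content of 14.3.1.3 to match the text.
4. If a promised summary is deliberately dropped, record it in SAP section 3.

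The cost is SAP wording and one or two extra tables from an existing template. The listing template already has columns for seriousness, action taken on study product and withdrawal, so no new data collection should be needed.

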5.1 Templates for the Tables, Listings and Figures

This is a guideline which will give the guidance of treatment labels that will be used for the table header and in the figures, listings and in the footnotes.

The treatment labels for the column heading will be as follow:

- Facial micellar cleanser
- Saline Solution

Document Name	gsk-207585-reporting-and-analysis-plan		
Type	Version	Document Identifier	Effective Date
eldo controlled	0.1; CURRENT; Most-Recent; Reviewed	090032d580e125d0	
Reason For Issue			

Protocol: 207585

Program Run Date:ddmonyyyy

Table 14.1.1
Subject Disposition
All Screened Subjects

All Screened Subjects (N=xx)

	overall(N=xx)
	n (%)
TOTAL NUMBER OF SUBJECTS SCREENED	xx (xx.x)
SUBJECTS NOT RANDOMISED	xx (xx.x)
DID NOT MEET STUDY CRITERIA	xx (xx.x)
ADVERSE EVENTS	xx (xx.x)
ETC.	xx (xx.x)
SUBJECTS RANDOMISED	xx (xx.x)
COMPLETED	xx (xx.x)
DID NOT COMPLETE	xx (xx.x)
ADVERSE EVENT	xx (xx.x)
LOST TO FOLLOW UP	xx (xx.x)
PROTOCOL DEVIATION	xx (xx.x)
WITHDRAWAL OF CONSENT	xx (xx.x)
OTHER	xx (xx.x)
RANDOMISED POPULATION	xx (xx.x)
SAFETY POPULATION	xx (xx.x)
INTENT TO TREAT POPULATION	xx (xx.x)

Page x of y

PPD

Document Name	gsk-207585-reporting-and-analysis-plan		
Type	Version	Document Identifier	Effective Date
elido_controlled	0.1; CURRENT; Most-Recent; Reviewed	090032d580e125d0	

Protocol: 207585

Program Run Date:ddmonyyyy

Table 14.1.2.1
Subject Demographics and Baseline Characteristics
Safety Population

Safety Population (N=XX)

Demographic variables

overall

(N=XX)

SEX n (%)

xx (xx.x)

MALE

xx (xx.x)

FEMALE

RACE n (%)

xx (xx.x)

ASIAN

xx (xx.x)

BLACK or AFRICAN

xx (xx.x)

AMERICAN INDIAN OR ALASKA NATIVE

xx (xx.x)

NATIVE HAWAIIAN OR OTHER PACIFIC ISLANDER

xx (xx.x)

WHITE

xx (xx.x)

MULTIPLE

xx (xx.x)

AGE (YEARS)

xx

N

xx.x

MEAN

xx.xx

SD

xx.x

MEDIAN

xx

MINIMUM

xx

MAXIMUM

xx

FITZPATRICK SCALE FOR SKIN TYPE

I= ALWAYS BURNS EASILY NEVER TANS (PALE WHITE SKIN);

xx (xx.x)

II= ALWAYS BURNS EASILY; TANS MINIMALLY (WHITE SKIN);

xx (xx.x)

III= BURNS MODERATELY; TANS GRADUALLY (LIGHT BROWN SKIN);

xx (xx.x)

IV= BURNS MINIMALLY, ALWAYS TANS WELL (MODERATE BROWN SKIN);

xx (xx.x)

V= RARELY BURNS, TANS PROFUSELY (DARK BROWN SKIN);

xx (xx.x)

VI= NEVER BURNS (DEEPLY PIGMENTED DARK BROWN TO BLACK SKIN)

xx (xx.x)

Document Name	gsk-207585-reporting-and-analysis-plan		
Type	Version	Document Identifier	Effective Date
eldo_controlled	0.1; CURRENT; Most-Recent; Reviewed	090032d580e125d0	
Reason For Issue			

Protocol: 207585

Program Run Date:ddmonyyyy

Table 14.2.1.1
Frequency of Combined Score by Phase, Visit and Treatment and Maximum Combined Score
Intent to Treat Population

Intent to Treat Population (N=XX)

Phase: Induction Phase

Visit	Combined Scores	Facial micellar cleanser		Saline Solution	
		(N=XX)	n	(N=XX)	n
Subjects with at least one combined score > 0 at any visit n (%)		xx (xx.x)		xx (xx.x)	
Subjects with no combined score > 0 at any visit n (%)		xx (xx.x)		xx (xx.x)	
VISIT 2	0	xx		xx	
	1	xx		xx	
	2	xx		xx	
	3	xx		xx	
	4	xx		xx	
	5	xx		xx	
	6	xx		xx	
	7	xx		xx	
VISIT 3		xx		xx	
		xx		xx	
		xx		xx	
VISIT 10		xx		xx	
		xx		xx	
MAXIMUM COMBINED SCORE	1	xx		xx	
	2	xx		xx	
	3	xx		xx	
	4	xx		xx	
	5	xx		xx	
	6	xx		xx	
	7	xx		xx	

Combined Score: Dermal response Score + Superficial response score (>0)

Page x of y

PPD

Programming Note:

- Induction Phase include visit 2 till visit 10.
- Rest Phase include Visit 11
- Challenge Phase include visit 12 till visit 15
- This table is only required if at least one subject reports a combined score >0
- Maximum combined Score will be calculated and displayed at the end of each phase irrespective of visits.

Document Name	gsk-207585-reporting-and-analysis-plan		
Type	Version	Document Identifier	Effective Date
eldo_controlled	0.1; CURRENT; Most-Recent; Reviewed	090032d580e125d0	
Reason For Issue			

Protocol: 207585

Program Run Date:ddmonyyyy

Table 14.2.2.1
Frequency of Dermal Response Score by Phase, Visit and Treatment and Maximum Dermal Response Score
Intent to Treat Population

Intent to Treat Population (N=XX)

Phase: Induction Phase

Visit	Score	Facial micellar cleanser	Saline Solution
		(N=XX)	(N=XX)
		n	n
Subjects with at least one dermal response score > 0 at any visit n (%)		xx (xx.x)	xx (xx.x)
Subjects with no dermal response score > 0 at any visit n (%)		xx (xx.x)	xx (xx.x)
VISIT 2			
0		xx	xx
1		xx	xx
2		xx	xx
3		xx	xx
4		xx	xx
5		xx	xx
6		xx	xx
7		xx	xx
VISIT 3			
VISIT 4			
.....			
VISIT 10			
MAXIMUM DERMAL RESPONSE SCORE		xx	xx
.....			

0 = No evidence of irritation; 1= Minimal erythema barely perceptible; 2 = Definite erythema; readily visible;or minimal edema; minimal popular response; 3 = Erythema and papules;4 = Definite edema; 5 = Erythema, edema and papules; 6 = Vesicular eruption; 7 = Strong reaction spreading beyond test site

Page x of y

Programming Note:

- Induction Phase include visit 2 till visit 10.
- Rest Phase include visit 11
- Repeat for the challenge phase.
- Challenge Phase include visit 12 till visit 15
- This table is only required if at least one subject reports a dermal response score >0
- Maximum dermal response Score will be calculated and displayed at the end of each phase irrespective of visits.

Document Name	gsk-207585-reporting-and-analysis-plan		
Type	Version	Document Identifier	Effective Date
eldo_controlled	0.1; CURRENT; Most-Recent; Reviewed	090032d580e125d0	
Reason For Issue			

Protocol: 207585

Program Run Date:ddmonyyyy

Table 14.2.2.2
Frequency of Superficial Irritation (other effects) Score by Phase, Visit and Treatment and Maximum Superficial Irritation (other effects) Score
Intent to Treat Population

Intent to Treat Population (N=XX)

Phase: Induction Phase

Visit	Grade/Score	Facial micellar cleanser	Saline solution
		(N=XX)	(N=XX)
		n	n
Subjects with at least one superficial irritation score > 0 at any visit n (%)		xx (xx.x)	xx (xx.x)
Subjects with no superficial irritation score > 0 at any visit n (%)		xx (xx.x)	xx (xx.x)
VISIT 2			
	GRADE=A/SCORE=0	xx	xx
	GRADE=B/SCORE=1	xx	xx
	GRADE=C/SCORE=2	xx	xx
	GRADE=F/SCORE=3	xx	xx
	GRADE=G/SCORE=3	xx	xx
	GRADE=H/SCORE=3	xx	xx
VISIT 3		
VISIT 4		
.....			
VISIT 10		
MAXIMUM SUPERFICIAL IRRITATION SCORE	xx	xx

A/0 = Slight glazed appearance; B/1 = marked glazing; C/2 = Glazing with peeling and cracking; F/3 = Glazing with fissures' G/3 = Film of dried serous exudate covering all or portion of the patch; H/3 = Small petechial erosions and/or scabs

Page x of y

PPD

Programming Note:

- Induction Phase include visit 2 till visit 10.
- Rest Phase include Visit 11
- Repeat for the challenge phase.
- Challenge Phase include visit 12 till visit 15
- This table is only required if at least one subject reports a superficial irritation score >0

Document Name	gsk-207585-reporting-and-analysis-plan		
Type	Version	Document Identifier	Effective Date
eldo_controlled	0.1; CURRENT; Most-Recent; Reviewed	090032d580e125d0	
Reason For Issue			

- Maximum superficial irritation Score will be calculated and displayed at the end of each phase irrespective of visits.

Document Name	gsk-207585-reporting-and-analysis-plan		
Type	Version	Document Identifier	Effective Date
elido_controlled	0.1; CURRENT; Most-Recent; Reviewed	090032d580e125d0	
Reason For Issue			

Protocol: 207585

Program Run Date:ddmonyyyy

Table 14.3.1.1
Summary of Treatment emergent Adverse Event
Safety Population

Safety Population (N=xx)	System Organ Class Preferred Term	Facial micellar cleanser	Saline Solution	
		(N=XX)	(N=XX)	nAE
NUMBER OF SUBJECTS WITH AT LEAST ONE AE	xx (xx.x)	xx	xx (xx.x)	xx
NUMBER OF SUBJECTS WITH NO AE	xx (xx.x)	xx	xx (xx.x)	xx
SKIN RELATED AES	xx (xx.x)	xx	xx (xx.x)	xx
SKIN AND SUBCUTANEOUS TISSUE DISORDERS	xx (xx.x)	xx	xx (xx.x)	xx
ERYTHEMA	xx (xx.x)	xx	xx (xx.x)	xx
DERMATITIS	xx (xx.x)	xx	xx (xx.x)	xx
NON SKIN RELATED AES	xx (xx.x)	xx	xx (xx.x)	xx
GASTROINTESTINAL SYSTEM	xx (xx.x)	xx	xx (xx.x)	xx
ABDOMINAL PAIN	xx (xx.x)	xx	xx (xx.x)	xx
DRY MOUTH	xx (xx.x)	xx	xx (xx.x)	xx
VOMITTING	xx (xx.x)	xx	xx (xx.x)	xx

n (%) = Number (percent) of subjects nAE = Number of adverse events.

Page x of y

PPD

Document Name	gsk-207585-reporting-and-analysis-plan		
Type	Version	Document Identifier	Effective Date
elido_controlled	0.1; CURRENT; Most-Recent; Reviewed	090032d580e125d0	
Reason For Issue			

Protocol: 207585

Program Run Date:ddmonyyyy

 Table 14.3.1.2
 Summary of Treatment emergent Adverse Event by Severity
 Safety Population

Safety Population (N=xx)	System Organ Class Preferred Term	Facial micellar cleanser (N=xx)						Saline solution (N=xx)					
		Mild		Moderate		Severe		Mild		Moderate		Severe	
		n (%)	nAE	n (%)	nAE	n (%)	nAE	n (%)	nAE	n (%)	nAE	n (%)	nAE
NUMBER OF SUBJECTS WITH AT LEAST ONE AE		xx (xx.x)	xx	xx (xx.x)	xx	xx (xx.x)	xx	xx (xx.x)	xx	xx (xx.x)	xx	xx (xx.x)	xx
NUMBER OF SUBJECTS WITH NO AE		xx (xx.x)	xx	xx (xx.x)	xx	xx (xx.x)	xx	xx (xx.x)	xx	xx (xx.x)	xx	xx (xx.x)	xx
SKIN RELATED AES		xx (xx.x)	xx	xx (xx.x)	xx	xx (xx.x)	xx	xx (xx.x)	xx	xx (xx.x)	xx	xx (xx.x)	xx
SKIN AND SUBCUTANEOUS TISSUE DISORDERS		xx (xx.x)	xx	xx (xx.x)	xx	xx (xx.x)	xx	xx (xx.x)	xx	xx (xx.x)	xx	xx (xx.x)	xx
ERYTHEMA		xx (xx.x)	xx	xx (xx.x)	xx	xx (xx.x)	xx	xx (xx.x)	xx	xx (xx.x)	xx	xx (xx.x)	xx
DERMATITIS		xx (xx.x)	xx	xx (xx.x)	xx	xx (xx.x)	xx	xx (xx.x)	xx	xx (xx.x)	xx	xx (xx.x)	xx
NON SKIN RELATED AES		xx (xx.x)	xx	xx (xx.x)	xx	xx (xx.x)	xx	xx (xx.x)	xx	xx (xx.x)	xx	xx (xx.x)	xx
GASTROINTESTINAL SYSTEM		xx (xx.x)	xx	xx (xx.x)	xx	xx (xx.x)	xx	xx (xx.x)	xx	xx (xx.x)	xx	xx (xx.x)	xx
ABDOMINAL PAIN		xx (xx.x)	xx	xx (xx.x)	xx	xx (xx.x)	xx	xx (xx.x)	xx	xx (xx.x)	xx	xx (xx.x)	xx
DRY MOUTH		xx (xx.x)	xx	xx (xx.x)	xx	xx (xx.x)	xx	xx (xx.x)	xx	xx (xx.x)	xx	xx (xx.x)	xx
VOMITTING		xx (xx.x)	xx	xx (xx.x)	xx	xx (xx.x)	xx	xx (xx.x)	xx	xx (xx.x)	xx	xx (xx.x)	xx

n (%) = Number (percent) of subjects nAE = Number of adverse events.

Page x of y

PPD

Document Name	gsk-207585-reporting-and-analysis-plan		
Type	Version	Document Identifier	Effective Date
eldo_controlled	0.1; CURRENT; Most-Recent; Reviewed	090032d580e125d0	

Protocol: 207585

Program Run Date:ddmonyyyy

Listing 16.1.7
Randomisation information
Randomised Population

Subject Number	Age/Sex/Race[1]	Randomisation Number	Test Site/Treatment Randomised	Date of randomization
PPD				

[1] Age in years; Sex: F = Female, M = Male; Race: A = Asian, B = Black or African American, I = American Indian or Alaska Native, H = Native Hawaiian or Other Pacific Islander, W = White, O = Multiple.

Page x of y

PPD

Document Name	gsk-207585-reporting-and-analysis-plan		
Type	Version	Document Identifier	Effective Date
eldo_controlled	0.1; CURRENT; Most-Recent; Reviewed	090032d580e125d0	

Protocol: 207585

Program Run Date:ddmonyyyy

Listing 16.2.2
Individual Subjects Protocol Violation
Randomised Population

Subject Number	Age/Sex/Race[1]	Phase/Visit # [2]	Violation Sequence	Protocol Violation	
PPD					

[1] Age in years; Sex: F = Female, M = Male ; Race: A = Asian, B = Black or African American, I = American Indian or Alaska Native, H = Native Hawaiian or other Pacific Islander, W = White, O = Multiple.

[2] Induction phase: Visit 2 till Visit 10; Rest: Visit 11; Challenge phase: Visit 12 till visit 15.

Page x of y

PPD

■

Document Name	gsk-207585-reporting-and-analysis-plan		
Type	Version	Document Identifier	Effective Date
eldo_controlled	0.1; CURRENT; Most-Recent; Reviewed	090032d580e125d0	

Protocol: 207585

Program Run Date: ddmonyyyy

Listing 16.2.7.1
All Adverse Events
Randomised Population

Treatment Group: Facial micellar cleanser

Subject Number	Age/Sex/Race [1]	Adverse Event (Preferred Term) (System Organ Class)	Start Date /Study Day [2]	Start Time	End Date	End Time	Frequency /Intensity [3]	Related to Study Product?	Action Taken re Study Product	Outcome	Serious ?	Withdrawn? [4]
PPD												

[1] Age in years; Sex: F = Female, M = Male ; Race: A = Asian, B = Black or African American, I = American Indian or Alaska Native, H = Native Hawaiian or Other Pacific Islander, W = White, O = Multiple.

[2] Study day is the day relative to start of treatment, day 1 being the day of first treatment.

[3] INT = Intermittent and SGLE = Single.

[4] Did subject withdraw from study as a result of this adverse event?

Page x of y

PPD

Programming Note:

- Repeat the same layout for the listing 16.2.7.2
- Population should be used 'Non randomised Subjects'
- The fourth column should be only 'Start Date'
- Delete the footnote related to study day and adjust the numbers accordingly.
